2. Potential subjects will be pre-qualified by a 6-item questionnaire, the Questionnaire for Urinary Incontinence Diagnosis (QUID) (4). This questionnaire has 3 questions each referring to the seriousness of Stress Urinary Incontinence (SUI) and of Urge Urinary Incontinence (UUI). Subjects will be accepted if their SUI score is 5 or greater and is greater than the UUI score. For privacy reasons, these scores will not be retained. Subjects will then be given an appointment. Subjects will be instructed to wear comfortable athletic type wear and not to drink any fluid for two hours prior to their appointment.
3. When they appear for their appointment, subjects will be administered the informed consent. All paperwork will be pre-numbered with a code that will link to the subject name. They key will be kept confidential by the Study Coordinator. They will be instructed to empty their bladders and will be given a liter of water or other drink and instructed to drink it over a 15-20 minute time period. An abbreviated patient history will be obtained for the purpose of establishing whether the subject meets the inclusion criteria and is not disqualified by meeting the exclusion criteria. The subject will again fill out the QUID questionnaire. The inclusion criteria are a SUI score of 5 or greater, predominately SUI (SUI score>UUI score) and age between 25 and 65. Exclusion criteria are predominantly UUI, prolapse greater than mild, hysterectomy or other pelvic floor surgery other than a Caesarian section, diabetes, BMI>35 or unable to perform ten

“jumping jack” exercises. Patients will be administered three additional questionnaires in order to compute a Severity Score. These questionnaires are the Urinary Distress Inventory (UDI), Urinary Impact Questionnaire (UIQ) and the Incontinence Severity Index (ISI). The scores will be multiplied together to provide the Severity Score.

4. Patients will then participate in an abbreviated Pad Test. This test has been validated (5). An hour after finishing the liter of liquid, the subject is given a tared incontinence pad, which is then put in place. She then engages in the following mild exercise challenges..
 - a. Stand from sitting 10 times.
 - b. Cough vigorously while standing.
 - c. Bend down to pick up small object.
 - d. Perform ten jumping jacks.

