The subject then will remove pad, place into bag and seal. The Experimenter will then weigh pad. The subjects will be randomized so that half will perform the Abbreviated Pad Test with the Yoni.Fit device in place followed by repeating without the device in place. The other half will perform the challenges in the reverse order.

5. The experimenter will calculate a change in score, which is the weight of the pad worn without the device in place minus the tare weight of the pad divided by the weight of the pad with the device in place minus the tare weight of the pad. In case no urine is released with the device in place, the Improvement Score will be defined as “1000”. A Release Change will also be calculated as the net weight without the device in place minus the weight with the device in place divided by the net weight released without the device in place.
6. Patients will be paid \$100 for their participation.

Data Analysis

After checking the data for correctness, the data analysis will ensue. Descriptive statistics will be calculated and include the mean, median, standard deviation. The improvement scores will be correlated with the symptom scores and demographics to provide a preliminary estimate of how well the YoniFit performs and possibly to identify parameters that predict less than optimal prevention of SUI.

Budget

Item	Amount
Personnel	
[name], PI	\$9,251
[name], Clinical Coordinator	\$3,989
Per subject costs	\$38,250
IRB application and account set-up	\$3,000
Supplies and Miscellaneous Costs	\$1,000
Total direct cost	\$55,490
Clinical trial IDC (30%)	\$16,647
Grand Total cost	\$72,137

Budget Justification

[name] will act as overall PI for this project and will coordinate between Watkins-Conti Products and the OUHSC. He will meet with the clinicians as necessary and weekly with [name] to assess progress and solve any problems. He will also be responsible for preparing the IRB application and for the data analysis and for preparing a report. His cost is calculated on the basis of 1 person-month (8.33% effort) on a University salary of \$80,457 plus 37.98% fringe benefits.

[name] will act as the clinical coordinator. In addition to the per subject costs, she will also assist with preparing the IRB application, talk to patients who do not qualify, coordinate with the physicians and meet with [name]. Her cost is calculated on the basis of a salary of \$28,907 with 10% effort plus 37.98% fringe

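### Release Change has no value for a woman who is dry without the device, no rule covers this, and its planned median and mean can mislead in opposite directions

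*Combined protocol and SAP*

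**What the plan says.** Protocol step 5 defines two per-woman measures from the same two pad weights.

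- The change in score, which the plan then calls the Improvement Score, is the ratio of the two net weights, with the without-device leak on top and the with-device leak below. It has a rule for a zero denominator: "In case no urine is released with the device in place, the Improvement Score will be defined as “1000".
- Release Change takes the difference between those two weights as its numerator, and this is "divided by the net weight released without the device in place". It has no rule for a zero denominator.

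Step 3 sets entry by questionnaire and age: "The inclusion criteria are a SUI score of 5 or greater, predominately SUI (SUI score>UUI score) and age between 25 and 65". Neither the inclusion nor the exclusion criteria require a measurable leak on the pad test. Step 4 randomizes the order of testing, with this split: "half will perform the Abbreviated Pad Test with the Yoni.Fit device in place followed by repeating without the device in place". Everyone else is tested the other way round.

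The Data Analysis section states: "Descriptive statistics will be calculated and include the mean, median, standard deviation". It also plans to correlate improvement scores with symptom scores and demographics. It does not say how an undefined value is handled.

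**The concern.** The plan foresaw a zero denominator for one score but not for the other. A woman can qualify on her questionnaire answers and still be dry on a short pad test. For the half tested with the device first, the without-device test could not serve as a screen even if one were intended.

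The gap is not neutral. A change from wet to dry counts in full at +100%. A change from dry to wet has no value. A mean or standard deviation cannot contain an undefined number, so leaving such women out is the likely default unless a rule is written. What remains is selected on the without-device test being positive.

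The background section names reduced or eliminated leakage as the primary endpoint and says the results are to support funding applications. Release Change is the step 5 measure that expresses a reduction as a fraction. A rule chosen after the data are seen would also be open to question.

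**Working it through.** **Notation.** W0 is the net pad weight without the device and W1 the net weight with it. Step 5 writes only weight for the with-device term of Release Change; I read it as net.

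- Release Change: RC = (W0 - W1)/W0
- Improvement Score: IS = W0/W1, or 1000 if W1 = 0

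The plan states no figure to reproduce, so the check starts from the formulas.

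**Step 1: the possible cases (illustrative grams).**

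| W0 | W1 | RC | IS | W0 - W1 |
|---|---|---|---|---|
| 10 | 2 | +0.8 | 5 | 8 |
| 10 | 0 | +1.0 | 1000 | 10 |
| 5 | 10 | -1.0 | 0.5 | -5 |
| 1 | 10 | -9.0 | 0.1 | -9 |
| 0.1 | 10 | -99 | 0.01 | -9.9 |
| 0 | 10 | undefined | 0 | -10 |
| 0 | 0 | undefined | 1000 | 0 |

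RC is lost only when W0 = 0. Its upper limit is +1 and it has no lower limit. The difference in grams exists in every row.

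**Step 2: how likely is at least one undefined value?** No sample size is stated. The Budget implies $38,250 / $765 = 50 women. Let p be the share with W0 = 0, which is an assumption. The chance of at least one is 1 - (1 - p)^50.

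| p | Expected undefined | Chance of at least one |
|---|---|---|
| 2% | 1 | 64% |
| 5% | 2.5 | 92% |
| 10% | 5 | 99% |
| 20% | 10 | >99.9% |

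**Step 3: effect on the summaries for a useless device.** I simulated pairs with identical distributions in both conditions: latent-normal pairs with correlation r, the lowest fraction dry, and a log-normal leak when wet. Dry rate, r and log-SD are all assumptions. Women with W0 = 0 are left out.

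At 20% dry and r = 0.5, 11.3% of women are dry without and wet with the device, and by symmetry 11.3% are the reverse. Those dry on both are 20 - 11.3 = 8.7%. Those kept are 80%. Of these, 11.3/80 = 14% score +100% by chance. The women wet on both tests are 100 - 11.3 - 11.3 - 8.7 = 68.7% and split evenly, so 34.35/80 = 43% of those kept have a negative RC and 57% a positive one. That moves the median above zero.

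Median RC at log-SD 1:

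| Dry rate | r = 0.5 | r = 0.7 | r = 0.9 |
|---|---|---|---|
| 10% | +10% | +7% | +2% |
| 20% | +21% | +13% | +5% |
| 30% | +31% | +20% | +7% |

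If dry-then-wet women are ranked worst and dry-on-both women as unchanged, the median returns to zero.

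The mean usually goes the other way, because small W0 gives extreme negative values. At 20% dry and r = 0.5:

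| log-SD | Median RC | Mean RC |
|---|---|---|
| 0.5 | +0.11 | -0.01 |
| 1.0 | about +0.21 | about -0.65 |
| 1.5 | +0.30 | -2.84 |

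At r = 0.9 (20% dry, log-SD 1) the median is between +4% and +5% and the mean about -13%.

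**Step 4: the alternative under the same model.** Group percent reduction, 1 - (sum of W1)/(sum of W0), is 0% over all women, within simulation error. Restricted to women with W0 > 0, it is about +7% (20% dry, r = 0.5, log-SD 1).

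**Step 5: a made-up example of 50 women.** Forty go from 10 to 2 g, five from 5 to 10 g, and five from 0 to 5 g. RC exists for 45 and keeps 5 of the 10 who worsened. The mean difference is (320 - 25 - 25)/50 = 5.4 g over all women and (320 - 25)/45 = 6.6 g over the 45.

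**The case against.** A reader might infer that Release Change drops the women who got worse, or that it always makes a useless device look effective. The documents support neither.

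- Any woman with a positive without-device leak who worsens keeps a negative value, with no lower bound. The women who lose a value also include those dry on both tests, who did not worsen.
- The plan does not say that undefined values are excluded. It is silent; exclusion is the likely default, not a stated rule.
- The mean, the first statistic listed, usually errs against the device. In 27 null scenarios (dry 10-30%, correlation 0 to 0.9, log-SD 0.5 to 1.5) it was positive in only 4, all at log-SD 0.5.
- A bias in the ratio of totals among women with a positive without-device pad is not a bias in anything planned, because the plan never computes that ratio.

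Other points also have weight. The dry-then-wet woman is not lost to the study: her Improvement Score is 0, its worst value, and the Data Analysis section names improvement scores for the correlations. Release Change is an additional measure and is not designated primary. The liter of fluid, the hour's wait, the coughing and the jumping jacks all make a dry without-device pad less likely. Two tests at one visit are probably well correlated, which shrinks the distortion. This is a feasibility study with descriptive analysis and no planned test.

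These points limit the size and reach of the problem. They do not supply a value for a woman with W0 = 0, and they do not stop the planned median and mean from pointing in opposite directions when the device does nothing.

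**Conclusion.** The point holds in a limited form. As written, Release Change cannot be computed when the without-device net weight is zero, entry does not prevent that, and no rule covers it. Wet-to-dry and dry-to-wet are therefore treated unequally. With undefined values left out, the planned median favours a useless device and the planned mean usually errs against it.

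The structural part rests on the documents alone. The sizes do not. The +21% and -65% need 20% dry, correlation 0.5 and log-SD 1, and the distortion falls sharply at correlation 0.9. The mean's size, and sometimes its sign, depends on the assumed spread of leak weights. Exclusion of undefined values is itself an assumption. The change is worth making before data are collected, but nothing here shows that the study would reach a wrong conclusion.

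**What to change.** In step 5 and the Data Analysis section:

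1. Define the paired difference in grams, net without minus net with device, for every woman with both pads, and make it the leakage-reduction measure.
2. Give percent reduction only for the group, as 1 minus total with-device leakage over total without-device leakage, with all women included.
3. For eliminated leakage, report the paired 2x2 table: wet to dry, dry to wet, wet on both, dry on both.

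If Release Change is kept as a descriptive extra, state in advance how a zero without-device weight is handled and report how many women have no value.

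The cost is a change of wording; the weights are already collected. There are two downsides. Grams give more weight to heavy leakers, and the reported effect may look less favourable because dry-to-wet women now count.

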Watkins-Conti Products, Inc., has developed a simple design that solves many of these problems and could provide a simple, inexpensive solution for SUI for many women. The Collapsible Cone-Shaped Intra-Vaginal Urinary Incontinence Support Device (Yoni.Fit) from 100% medical grade silicone, places pressure on the urethral sphincter while supporting pelvic organs, thus eliminating or significantly reducing urine leakage. Inspired by the ring pessary, the simple yet effective design of the collapsible device Yoni.Fit is user friendly, light weight and less difficult to hold in the vagina than the Colpexin. Yoni.fit is believed to assist with strengthening the pelvic floor like the Colpexin while supporting anatomy like the pessary, reducing the need for invasive surgeries altogether.

[figure not shown]
In order to support applications for Small Business Innovation Research funding and for investor funding, Watkins-Conti Products proposes to demonstrate short term efficacy with patients suffering from SUI for reduced or eliminated leakage against a standardized battery of challenges as a primary endpoint. Ease of use and support of anatomy with use of Yoni.Fit will serve as secondary endpoint

Specific Aims-
Aim: Test the acute efficacy of Yoni-Fit in a clinical trial of unselected women with incontinence in a standardized set of challenges performed with and without Yoni-Fit in place.

Protocol

The flow chart for the study is shown in the figure below.

Flow Chart for Feasibility Study

1. Subjects will be recruited in two ways. First, subjects will be referred from the patient bases of two physicians at the OUHSC who treat incontinence. These are [name] of the Department of Obstetrics and Gynecology and [name] of the Department of Urology. The second source will be a campus-wide email announcing the study. Regardless of the method, potential subjects will be referred to [name], a research coordinator for the study who is employed by the Department of Urology.

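### No effect size is tied to the leakage endpoint; the 1000 code makes the mean Improvement Score unusable, and mean Release Change can be biased

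*Combined protocol and SAP*

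**What the plan says.** The Background section says that the sponsor wants to "demonstrate short term efficacy with patients suffering from SUI for reduced or eliminated leakage against a standardized battery of challenges as a primary endpoint". The leakage data come from a pad test done twice by each woman, with order randomised: "half will perform the Abbreviated Pad Test with the Yoni.Fit device in place followed by repeating without the device in place", and the other half the reverse (Protocol, step 4).

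Step 5 turns the two net weights into two ratios per woman. The first, called a change in score and then the Improvement Score, is a quantity "which is the weight of the pad worn without the device in place minus the tare weight of the pad divided by the weight"; the divisor is the device pad's weight, again net of tare. A dry device pad has its own rule: "In case no urine is released with the device in place", the score is set to 1000. The second ratio is introduced thus: "A Release Change will also be calculated as the net weight without the device in place minus the weight with the device in place", with the net weight without the device as divisor. No rule covers a divisor of zero.

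Data Analysis then says "Descriptive statistics will be calculated and include the mean, median, standard deviation". It does not say of which variable, or which summary answers the primary endpoint. Its next sentence correlates the improvement scores with symptom scores and demographics "to provide a preliminary estimate of how well the YoniFit performs". No test, confidence interval or success threshold is given.

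Entry rests on questionnaires and age: "The inclusion criteria are a SUI score of 5 or greater, predominately SUI (SUI score>UUI score) and age between 25 and 65" (step 3). The exclusion criteria set no minimum pad-test leakage either.

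**The concern.** The product of this study is an effect size, intended to support funding applications. The plan leaves that effect size unchosen and puts its performance claim on a correlation. A correlation shows whether the score varies with symptoms or demographics. It does not show how much leakage falls.

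That leaves the listed summaries, and the mean is among them. Taking them to apply to the two ratios is the natural reading, though not a stated one. Averaged, the 1000 code is treated as a measured thousand-fold improvement. Because no minimum leakage is required, a woman may also be dry on both tests. She has shown no benefit, yet she scores 1000. If the summary is chosen after the data are seen, one dataset can yield very different headline figures.

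**Working it through.** **Inputs.** Let A be net leakage without the device and B net leakage with it. The score is A/B and Release Change is 1 − B/A (step 5). The plan states no sample size. The Budget gives 38,250 dollars of per-subject costs and the Budget Justification 765 dollars per woman, so N = 38,250/765 = 50. Repeatability, period effect and dry-pad rate are not given and are assumed below. There is no planned effect size to reproduce.

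**1. The 1000 code (no noise assumption needed).**
- 49 women unchanged (score 1), 1 dry with the device: (49 × 1 + 1000)/50 = 20.98. Each such woman adds (1000 − 1)/50 = 19.98.
- 49 women with leakage halved (score 2), 1 dry: (98 + 1000)/50 = 21.96.
- 45 women halved, 5 dry: (90 + 5000)/50 = 101.8.

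In the last two cases the median stays at 2.0. The mean essentially reports 1000 times the dry fraction. The median is no complete safeguard: with 25 of 50 dry and 25 at a score of 2, it is (2 + 1000)/2 = 501.

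**2. Mean score with every pad wet.** Two women, one 10 g without and 5 g with, the other 5 g without and 10 g with, leak the same in total (15 g and 15 g). Their mean score is (2 + 0.5)/2 = 1.25, and their mean Release Change is (0.5 − 1)/2 = −0.25. In general, with independent lognormal test-retest errors of coefficient of variation CV and a useless device, E[A/B] = 1 + CV². That is 1.01, 1.09 and 1.25 at CV 0.1, 0.3 and 0.5.

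If leakage on the second test is multiplied by k, balanced order gives a further factor (k + 1/k)/2, which exceeds 1 unless k = 1. For an assumed k = 2 the factor is 1.25. Randomised order therefore does not remove a period effect from a mean of ratios.

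**3. Mean Release Change.** With true reduction r, all pads wet and no period effect, E = 1 − (1 − r)(1 + CV²).
- CV = 0: exactly r.
- r = 50%, CV 0.3: 1 − 0.5 × 1.09 = 45.5%.
- r = 50%, CV 0.5: 1 − 0.5 × 1.25 = 37.5%.

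With dry pads the error can go the other way. Suppose 10% of pads are dry at random on each test, the device is useless, and women dry without it are excluded. Then E = 0.1 × 1 + 0.9 × (−CV²), which is +9.1%, +1.9% and −12.5% at CV 0.1, 0.3 and 0.5, against −1%, −9% and −25% with wet pads. Women dry without the device but wet with it are dropped, while women dry only with it count as 100%.

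**4. Overall percent reduction.** Take each order group's mean weights with and without the device, and compute 1 − (sum of the two with-device means)/(sum of the two without-device means). Let m be the expected leakage on a first test without the device. The with-device means are then (1 − r)m and (1 − r)km, and the without-device means are km and m. The ratio is (1 − r)(1 + k)/(1 + k) = 1 − r, so k cancels even if the groups are unequal.

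In simulations of 50 women (4,000 trials per case, CV 0.1 to 0.5, k = 1 or 2, up to 10% dry pads, several order splits), this estimate averaged −3% to 0% for a useless device and 48% to 50% for a true halving. Its percentile bootstrap interval covered 89% to 94%.

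**5. Bootstrap interval for the median score.** Medians were taken within order groups and combined as the square root of their product (25 per order, CV 0.3, no period effect, score 2 in wet women). The upper limit exceeded 20 in about 20% of trials at 20% dry with the device and 74% at 30% dry, where it was typically about 50. The 1000 code thus enters the interval well before half the women are dry.

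**The case against.** The strongest reply is that the plan commits to no mean. The median is listed beside it, the study is labelled a feasibility study, and without a test or decision rule no false-positive conclusion is built in. That stands, and it limits the harm to a wrong effect size being quoted. It does not supply the missing choice of summary.

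A reader might infer that the mean of either ratio must give a wrong answer. The documents do not support that for Release Change. Its mean is a recognisable quantity, the average individual reduction, and the 1000 code does not touch it. If the spread were only true differences in response between women, it would be correct. With wet pads its noise error runs against the device, and it is small when the true reduction is large: at a log-scale test-retest SD of 0.25, a true 80% reads 79%.

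A reader might also infer that a period effect is present. The readable text states no refill or interval before the repeat test, but the flow chart is not available here and may give one. Step 4 calls the pad test validated, though it gives no repeatability figure. The period-effect results are therefore illustrations of an assumption.

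**Conclusion.** The point holds. No summary is tied to the primary endpoint, and the analysis that is said to estimate performance cannot give an effect size. The mean Improvement Score is unusable under the plan's own 1000 rule: about 20 is added per woman dry with the device, given the 50 women that the budget implies. That result needs no assumption about noise. The smaller upward bias with wet pads does depend on the assumed CV.

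For Release Change the supported statement is weaker: its mean can be biased, in either direction depending on noise and dry pads, and it has no value for a woman dry without the device. The size of that bias cannot be known from the documents. This should be settled before the data are seen.

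**What to change.** Reword step 5 and Data Analysis as follows.

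- **Primary.** Name one effect size in advance: the overall percent reduction, 1 − (net weight with / net weight without), from the sum of the two order-group mean weights. Give a bootstrap interval that resamples women within order group. This uses every woman and needs neither the 1000 code nor a zero-denominator rule.
- **Improvement Score.** Do not use its mean as the efficacy estimate, and do not treat 1000 as a number. Report the median by order group as secondary, with 1000 as a top rank only. Leave out and count women dry on both tests. Give no bootstrap interval when many women are dry with the device; the code enters the interval from about 20% to 30% dry.
- **Dry pads and Release Change.** Report the number dry on each test, and the median Release Change with the number excluded, noting that exclusion biases it upward.
- **Correlations.** Use rank correlation, so that 1000 acts only as a rank, and do not describe the result as the estimate of performance.

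No new data are needed. The price is that the overall reduction gives more weight to women with heavy leakage, and that its percentile bootstrap interval covers somewhat less than 95% at 50 women (about 89% to 94% in the simulations).
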